10.2. Treatments Administered

Eligible patients in the eteplirsen-treated group will receive a weekly 30-mg/kg dose of eteplirsen as an IV infusion for up to 96 weeks.

The dose of eteplirsen will be calculated based on the most recent patient weight obtained at the site prior to the current visit. Eteplirsen should be prepared for dosing by following the steps detailed in the study-specific Pharmacy Manual.

Eteplirsen will be administered as an IV infusion over a period of approximately 35 to 60 minutes. It is recommended that a topical anesthetic cream (eg, lidocaine 2.5%, prilocaine 2.5%, or LMX4 cream) be applied to the infusion site prior to each administration of eteplirsen. Additional administration and IP details are available in the study-specific Pharmacy Manual.

An implanted venous access port may be inserted for eteplirsen administration at the discretion of the Investigator. If eteplirsen is administered into an existing IV line, the line should be flushed with normal saline before and after administration of eteplirsen. After eteplirsen administration and the saline flush, the port may be flushed with heparin to heplock the port prior to removal of the infusion line.

No other medications may be administered concomitantly during the eteplirsen infusion.

All treated patients will be observed for at least 1 hour following the end of each eteplirsen infusion for the first year of treatment. If the patient has not experienced an infusion reaction after the first year of treatment, patients may be observed for at least 30 minutes following the end of each eteplirsen injection.

In-home study treatment administration by a visiting nurse may be available after Week 48.

The following guidelines for the timing of dosing should be followed throughout the study:

1. Patients should receive eteplirsen once every 7 days starting on Study Day 1. A window of ± 3 days from the scheduled dose is acceptable after the first infusion.

2. Patients may not receive 2 separate doses of eteplirsen within the same 60-hour period.
3. The medical monitor should be contacted in the event of ≥ 2 consecutive missed doses.

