12.4. Recording Adverse Events

All AEs/SAEs experienced from the time of informed consent to the last follow-up will be recorded within each patient's CRF. Information should include: a concise description of the event; date and time of event onset and resolution; determination of seriousness, severity, corrective treatment, outcome, and relationship to IP or study procedure or underlying disease; and any action taken will be recorded. Resolution occurs when the patient has returned to his baseline state of health or further improvement or worsening of the event is not expected.

Whenever possible, a diagnosis will be recorded as an AE, rather than symptoms or isolated laboratory abnormalities related to that diagnosis. Several symptoms or laboratory results that are related to the same diagnosis can thus be part of the same AE. A medical or surgical procedure is not an AE; rather the condition leading to the procedure should be recorded as the AE. Similarly, death is not an AE, but is rather the outcome of the AE(s) that resulted in death. If the AE(s) leading to death are not known, then death must be reported as an AE. All AEs will be followed until the resolution of AE, completion of the patient's study participation, or study termination, whichever occurs first. SAEs will be followed until resolution or until the condition stabilizes or returns to baseline status.

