4.2.2 Handling of Incomplete Dates

All available data will be included in data listings and tabulations.

An incomplete date will occur when the exact date an event occurred or ended cannot be obtained for a patient. Incomplete dates will be imputed as described below. No other imputation of missing data will be performed.

- For a partial or missing medication date, the medication will be classified as a concomitant medication unless the available part of the date indicates it is impossible for the drug to be concomitant. For example, if only the year for the

stop date is available and the year is prior to the year of dosing, the medication will be classified as a prior medication.

- For a partial AE onset date, the event will be classified as treatment emergent if the month and/or year of the onset date are on or after the initiation of eteplirsen for eteplirsen treated patients or after Day 1 for untreated patients and within 28 days of the last dose of eteplirsen for eteplirsen treated patients or within a day after last visit for untreated patients, or if the month and/or year of the onset date are on or after the date of the qualifying visit for untreated patients. All AEs with a missing AE onset date will be classified as treatment emergent.
- For the purpose of calculating the time since DMD diagnosis or duration of prior corticosteroid use, if the date of DMD diagnosis or the start date of corticosteroid use has a missing day but known month and year, then the 15th of the month will be used in the calculation. If the date has a missing day and month and only the year is known, December 31st of the recorded year will be used in the calculation.

In all cases, the original missing or incomplete dates will be presented in the data listings.

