5.8.2 Adverse Events of Special Interest

Summaries of TEAEs of special interest will be summarized by SOC and PT. All standard MedDRA queries (SMQs based on MedDRA version 17.1) listed below will include broad and narrow terms. The AEs of special interest (AESI) are:

- Hypersensitivity (hypersensitivity SMQ)
- Renal toxicity (acute renal failure SMQ)
- Infusion-related reaction (IRR) (AEs occurring within 24 hours of the start of any infusion [including events that occurred on the same date as an infusion where infusion start time or AE onset time was not reported])

For all IRRs as defined above, adjudicated IRRs will be identified by a pharmacovigilance physician. All IRRs as defined above that are considered as related to study drug by investigators will be counted in the list of adjudicated IRRs. In addition, all

IRRs as defined above that meet the following criteria will be excluded from the list of adjudicated IRRs:

- AE was an infusion site, application site, or other local AE not associated with IRR
- AE had a clear alternate etiology that could be ascertained based on the reported event (eg, reaction to plaster, assessed as related to procedure or underlying disease by investigator)
- AE not associated with an IRR due to the nature of the event or biologically implausible (eg, fibula fracture, chalazion)

A summary table will be generated and include the following:

- Number of patients with adjudicated IRRs
- Number of adjudicated IRRs
- Number of adjudicated IRRs with event start time reported
- Number of events on any day for adjudicated IRRs

A corresponding listing will be generated for each table. Additionally, a table and listing corresponding to the AESIs that were related to study drug or moderate or severe will be produced.

An overall summary of AESI events will include the total number of events, number of serious events, number of related events, number of not related events, number of mild events, number of moderate events, number of severe events, and number of events occurring on the same day as an infusion.

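### The missing-time rule for infusion-related reactions matches the infusion date, not the 24-hour window, so it can misclassify events in both directions

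*SAP*

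**What the plan says.** SAP 5.8.2 lists IRR as an adverse event of special interest. The definition is "AEs occurring within 24 hours of the start of any infusion", followed by a bracket for missing times: "including events that occurred on the same date as an infusion where infusion start time or AE onset time was not reported". The bracket applies if either of the two times is missing.

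Two later steps depend on that definition. The first is adjudication: "For all IRRs as defined above, adjudicated IRRs will be identified by a pharmacovigilance physician". The second is automatic: "All IRRs as defined above that are considered as related to study drug by investigators will be counted in the list of adjudicated IRRs". Three grounds then remove an event from the adjudicated list: a local reaction, a clear other cause, or an event that by its nature is not or could not be an IRR. None of the three concerns timing.

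No other visible rule deals with missing times. SAP 4.2.2 covers incomplete dates and adds "No other imputation of missing data will be performed". SAP 4.2.1 is blacked out, so this reading rests on the visible text.

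**The concern.** The definition is in elapsed hours and the fallback is in calendar dates. Unless an infusion starts at midnight, part of its 24-hour window lies on the following date. The fallback leaves that part out and takes in the hours of the infusion date before the infusion began.

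The two errors are handled differently. A wrongly admitted event at least reaches the adjudicating physician, who may remove it on one of the three grounds. A wrongly omitted event reaches nobody. The summary table has a row for "Number of adjudicated IRRs with event start time reported", so missing times are foreseen, but that row describes only events that were kept. The number left out is not visible.

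The situation is realistic. "All treated patients will be observed for at least 1 hour following the end of each eteplirsen infusion for the first year of treatment"; Protocol 10.2 allows 30 minutes later on if there has been no infusion reaction, and home infusion may be available after Week 48. Next-day events in children of 4 to 6 years would therefore usually be reported by caregivers. That these more often lack a clock time is a reasonable inference, not something the documents state. At stake is the count of a named event of special interest in a study whose primary objective is safety.

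**Working it through.** The plan states no IRR rate, missing-time share or onset pattern, so there is no figure to reproduce. The check follows one event through the rules and then does the clock arithmetic.

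**Inputs from the documents.** Window of 24 hours from infusion start and same-date fallback (SAP 5.8.2); no two doses within the same 60-hour period (Protocol 10.2).

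**Assumptions.** Infusion start at clock hour t; missing-time share m; true reactions with exponential onset of mean μ hours, cut off at 24 hours; background events spread evenly over the clock.

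**Step 1: route of a next-day event with no onset time.**
- Elapsed time cannot be computed, so the 24-hour test cannot be applied.
- The date is not the infusion date, so the bracket does not apply. The 60-hour rule means the next date cannot itself be an infusion date.
- Adjudication and the automatic count of related events both require the definition to be met first.

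The event is therefore left out. The same holds for a next-day event with a known onset time when the infusion start time is missing. This follows from the SAP's silence; the text does not expressly exclude such events.

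**Step 2: hours.** The true window is 24 − t hours on the infusion date plus t hours on the next date. The fallback covers 00:00 to 24:00 on the infusion date. It loses t post-infusion hours and admits t pre-infusion hours.

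| Start | Window hours lost | Share of window (t/24) | Pre-infusion hours admitted |
|---|---|---|---|
| 09:00 | 9 | 37.5% | 9 |
| 12:00 | 12 | 50% | 12 |
| 15:00 | 15 | 62.5% | 15 |

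**Step 3: true reactions falling on the next date.** With F(x) = 1 − exp(−x/μ), the share is L = [F(24) − F(24 − t)] / F(24). For t = 12 and μ = 6: F(24) = 0.9817, F(12) = 0.8647, so L = 0.1170 / 0.9817 = 11.9%. For μ = 2, L = 0.25%; for μ = 12, L = 26.9%. At μ = 6, L is 6.5% for a 09:00 start and 20.9% for 15:00.

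**Step 4: net change in the candidate count.** Let b be the background share of in-window events.
- Loss = m × [(1 − b)L + b·t/24]
- Gain = m × b·t/24
- Net = gain − loss = −m(1 − b)L

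For a 12:00 start:

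| b | m | μ = 2 h | μ = 6 h | μ = 12 h |
|---|---|---|---|---|
| 0 | 10% | −0.02% | −1.2% | −2.7% |
| 0 | 30% | −0.07% | −3.6% | −8.1% |
| 0.5 | 10% | −0.01% | −0.6% | −1.3% |
| 1 | 10% | 0 (−5% + 5%) | 0 | 0 |

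**Step 5: unequal missingness.** Step 4 uses one m for all events, which keeps the net at or below zero. If times are missing with share m₁ before the infusion on its date and m₂ on the next date, the net is m₁·b·t/24 − m₂[(1 − b)L + b·t/24]. For b = 0.5, t = 12 and μ = 6 it turns positive once m₁/m₂ exceeds 1 + (0.5 × 0.1192)/(0.5 × 0.5) = 1.24. If next-day times are missing more often, the under-count grows. The documents settle neither ratio.

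**Step 6: effect of adding the next date.** The two dates span 48 hours: 24 inside the window, t before it and 24 − t after it. For a 12:00 start that is 24, 12 and 12 hours.

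**The case against.** The case against has real weight.

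- Missing times should be the exception: Protocol 12.4 requires sites to record "date and time of event onset and resolution". The row for reported start times shows that gaps are foreseen, not that they are common.
- Omitted events stay in the safety analysis. Under SAP 5.8.1 they appear in the treatment-emergent tables, in the treatment-related tables if so rated, and in the listing of all adverse events. A term in the hypersensitivity query also remains an event of special interest, with no time limit. Only the IRR label is affected.
- Safety analyses are descriptive (SAP 5.8), and SAP 6.1 rules out any treated-versus-untreated comparison. No visible test or decision depends on the IRR count.

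All of this stands. It limits the consequence but does not reconcile the fallback with the definition.

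Three stronger readings are tempting and are not supported. A reader might infer that the IRR count is always biased low; the admitted pre-infusion events work the other way, and Step 5 shows that the sign can change. A reader might take the 37.5% to 62.5% in Step 2 as the share of IRRs lost; it is a share of clock hours under assumed start times, and it bears only on events with a missing time. A reader might suppose that the next date could simply be added because adjudication would remove late events. SAP 5.8.2 has no timing ground for exclusion and counts related events automatically, so a related event almost 48 hours after infusion start could be counted.

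**Conclusion.** The point holds as a mismatch between the IRR definition and its own missing-time rule. Next-day events that may lie within 24 hours have no route to adjudication, and same-date events that preceded the infusion are admitted. For true post-infusion reactions the rule can only lose cases. The net effect on the count has unknown direction and size.

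Under the illustrative assumptions of Step 4, the net change ranges from zero to about −8%, and it is close to zero if reactions begin within a few hours. These values rest on assumed start times, onset patterns and missing-time shares. The conclusion also assumes that the blacked-out SAP 4.2.1 contains no rule for missing times. The point is worth correcting because it touches a named event of special interest under the primary safety objective and is cheap to repair; it is not critical.

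**What to change.** In SAP 5.8.2:

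1. Reword the bracket so that, where either time is missing, events with onset on the infusion date or the following calendar date are possible IRRs, unless the known time or date shows that onset was before the infusion or more than 24 hours after its start. This follows the inclusive convention of SAP 4.2.2, where a medication with a partial date counts as concomitant unless the known part makes that impossible.
2. Send these events to the existing adjudicator, and let the adjudicator exclude next-day events judged to be outside 24 hours. State that related next-day events with a missing time are not counted automatically.
3. Report the adjudicated IRR count under the current same-date rule and under the extended rule, with the number of events with missing times.

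The cost is a short wording change, one extra count and a few more events to adjudicate. The downside is that some possible IRRs beyond 24 hours will enter the extended count, which is why both counts should be shown.

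### Do the SAP's two rules for adjudicated infusion-related reactions need an order of precedence?

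*SAP*

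**What the plan says.** SAP 5.8.2 names three adverse events of special interest (AESIs), one of which is IRR. IRR is defined by time alone: "AEs occurring within 24 hours of the start of any infusion", plus events on the same date as an infusion when a clock time is missing.

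From that pool, "adjudicated IRRs will be identified by a pharmacovigilance physician". Two rules follow. The inclusion rule is that "All IRRs as defined above that are considered as related to study drug by investigators will be counted in the list of adjudicated IRRs". The exclusion rule is that "IRRs as defined above that meet the following criteria will be excluded from the list of adjudicated IRRs". There are three exclusion criteria: local reactions at the infusion or application site; an alternative cause; and events whose nature makes an infusion reaction implausible. The second criterion asks for a "clear alternate etiology that could be ascertained based on the reported event", and one of its examples is an event "assessed as related to procedure or underlying disease by investigator".

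The adjudicated list feeds one summary table, whose first line is "Number of patients with adjudicated IRRs", and a listing.

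Protocol 12.3.1, 12.3.2 and 12.3.3 have the investigator rate each event's relationship to drug, to study procedures and to underlying disease as three separate judgements.

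**The concern.** Both rules apply to the whole 24-hour pool, neither limits the other, and no order is stated. The three relationship ratings are not mutually exclusive, so one event can be rated possibly related to the drug and also to a procedure or the disease. Read literally, the inclusion rule puts that event on the list and the exclusion rule takes it off. An event rated unrelated to drug that meets no exclusion criterion is covered by neither rule.

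Safety is the primary objective, and the adjudicated list is meant to separate true reactions from events that merely happened within a day of dosing. If two analysts could take the same data and report different numbers of boys with a reaction, that would matter in a group of about 20.

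A side issue concerns the dictionary. The standardised MedDRA queries (SMQs) in SAP 5.8.2 and 5.8.3 are fixed at version 17.1, while SAP 5.8 allows coding in 17.1 or a later version and the protocol synopsis refers to the current one.

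**Working it through.** This is a question of rule logic; the SAP gives no figure to reproduce.

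**Inputs.** Drug-related means rated possibly/probably or definitely related (SAP 4.8; protocol 12.3.1). Meeting any one exclusion criterion is taken as enough. About 20 treated boys are planned (SAP 3.3).

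**Step 1: the rules as written.** Two drug ratings × two criterion states = 4 classes.

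| Class | Drug rating | Exclusion criterion | Inclusion rule | Exclusion rule | Result |
|---|---|---|---|---|---|
| A | related | none met | in | silent | in |
| B | related | met | in | out | two answers |
| C | unrelated | met | silent | out | out |
| D | unrelated | none met | silent | silent | none stated |

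Two classes are settled, one has two answers and one has none. Taken literally, the list could run from A alone to A + B + D.

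**Step 2: which reading gives both rules a purpose?**

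- B in, D in: list A + B + D. Both rules do work.
- B in, D out: list A + B. The exclusion rule does nothing, since C would be out anyway.
- B out, D in: list A + D. The inclusion rule does nothing, since the list is simply whatever is not excluded.
- B out, D out: list A. Both rules do work.

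Only the first and last readings make sense of the section as a whole. Three features favour the first. The inclusion rule comes first and is unqualified. The examples given for exclusion (a reaction to plaster, a fracture, a chalazion) are events an investigator would seldom attribute to the drug; if all unrelated events were out by default, there would be little reason to list them. And the pool already carries the name IRR, so criteria that remove events from the list leave the remainder on it.

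**Step 3: how wide is class B?** The procedure or disease rating is an example within criterion 2, which requires a "clear alternate etiology that could be ascertained based on the reported event". An event the investigator thinks the drug may have caused does not readily have a clear other cause. Criteria 1 and 3 can be read as carrying their own test, that the event is not of an infusion-reaction kind, and the physician applies it. What remains is mainly a local event rated drug-related, or a dual-rated event where the example is applied mechanically.

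**Step 4: what could move?** Only the adjudicated-IRR table and its listing.

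- Class B events are drug-related by definition. They stay in the treatment-related event tables of SAP 5.8.1 and in the AESI output, where "a table and listing corresponding to the AESIs that were related to study drug or moderate or severe will be produced".
- Class D events stay in the AESI summary by system organ class and preferred term, with its listing, and in the overall AESI summary, which counts related and not-related events separately.
- A boy whose only qualifying event is contested changes the patient count by 1: 1/20 = 5 percentage points.

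**Step 5: the dictionary.** If coding is in 17.1, which SAP 5.8 permits, there is no mismatch. The documents do not show that a later version was used. Even if one was, liver and kidney chemistry, platelets, and ECG and ejection fraction are screened independently (SAP Appendix 1, Tables 1, 2 and 5). Hypersensitivity has no such second screen, but its events would still be in the general adverse event tables.

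**The case for a change.** The strongest case for a change is that the opposite reading is equally grammatical. The two readings that give both rules a purpose sit at the two ends of the range, A and A + B + D, so the choice between them is not trivial. The study is open-label, and the blinding described in SAP 3.1.2 does not extend to this adjudication. A physician can judge whether a criterion is met, but that judgement does not settle which rule wins once it is. One clause would remove the choice before anyone sees the counts.

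What stands is that no order is written down and that a dual-rated event can fall under both rules. What does not stand is that the result is left open in any way that matters. The section points to one reading, a named person applies it, and the three ratings are recorded for each event (protocol 12.4), so the count can be redone on the other reading.

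Nor does the size of the 24-hour pool help the objection. With weekly dosing the window covers 24/168 hours = 14.3% of treatment time, so about 1 in 7 coincidental events would enter the pool if onset were even over the week. That measures the whole pool, not classes B and D, and turning it into event counts needs an adverse event rate the documents do not give.

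**Conclusion.** No change is called for. SAP 5.8.2 leaves an order of precedence and a default class unwritten, and the adjudicating physician can supply both sensibly: drug-related events stay on the list, the exclusions filter the others, and what is not excluded remains. An added clause would record that reading without altering any other output.

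The possible effect is confined to one descriptive table and its listing. No test, analysis population or primary conclusion depends on it, and no event disappears from the safety report. Each boy with only a contested event is worth 5 percentage points of the planned treated group; the number of such boys cannot be derived from the documents.

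This rests on two assumptions: that any one exclusion criterion is enough, and that the physician reads the exclusion list in its ordinary sense. The dictionary point is hypothetical and vanishes if final coding is in MedDRA 17.1.
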